#### **16.1.1. ADVERSE EVENTS LEADING TO DISCONTINUATION FROM STUDY OR FROM TREATMENT**

Adverse events leading to permanent discontinuation from study will be identified by using the variable pertaining to outcome the Adverse Events page of the (e)CRF, and listed. AEs leading to discontinuation from treatment will be listed.

#### **16.1.2. SERIOUS ADVERSE EVENTS**

Serious adverse events (SAEs) are those events recorded as "Serious" on the Adverse Events page of the (e)CRF, and will be listed.

#### **16.1.3. DERIVATION**

Adverse Event	Intensity grade	Parameter
CCI - This section contained Clinical Outcome Assessment data collection questionnaires or indices, which are protected by third party copyright laws and therefore have been excluded.		

aFever is defined as temperature  $\geq 38.0^{\circ}\text{C}/100.4^{\circ}\text{F}$

### **16.2. SAFETY LABORATORY EVALUATIONS**

Laboratory results will be included in the reporting of this study for Hematology, Biochemistry and Urinalysis. A list of laboratory assessments to be included in the outputs is included in Appendix 4 of the protocol, Table 23.

For each group and for each haematology, biochemistry, and urinalysis parameter:

Document:	\\\usadc-nas01a\cp_ops\PROJECTS\Glaxo SmithKline\GSK208109_BZA47109\SAP		
Author:	PPD	Version Number:	3.0
		Version Date:	27SEP2021

Template No: CS\_TP\_BS016 – Revision 5  
Effective Date: 01Apr2018

Reference: CS\_WI\_BS005

- The percentage of subjects having hematology, biochemistry, and urinalysis results below or above the local laboratory normal ranges will be tabulated by timepoint
- The maximum grading from Screening up to Visit 5 (Day 61)/ Visit 7 (Day 390) for subjects receiving 2 doses/Visit 11 (Day 670) for subjects receiving a third dose will be tabulated.
- Frequency of Grade 3/4 laboratory toxicities will be summarized for subjects with COVID-19 infection.
- Individual profiles for each hematology and biochemistry parameter will be plotted by treatment group for which FDA grading scale is defined.

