3.0 OBJECTIVES AND ENDPOINTS

Table 9 Study Objectives and Endpoints

Objectives	Endpoints

Primary
 
 To evaluate the safety and reactogenicity profile of the C. difficile F2 fusion protein when administered with or without AS01B adjuvant as IM doses according to a 0, 1-month schedule, in healthy adults aged between 18-45 years and between 50-70 years followed by an additional dose administered approximately 15 months after Dose 2 in a subcohort of subjects aged 50-70 years, during the entire study period. 	
 Solicited local and general symptoms. 
 Occurrence of solicited local symptoms (any and Grade 3) within 7 days (Day 1 to Day 7) after each vaccination, in all subjects and in all groups. Occurrence of solicited general symptoms (any, Grade 3, related, and Grade 3 related) within 7 days (Day 1 to Day 7) after each vaccination, in all subjects and in all groups. Unsolicited AEs. 
 Occurrence of unsolicited AEs (any, Grade 3, related, Grade 3 related, and those resulting in a medically attended visit) within 30 days (Day 1 to Day 30) after each vaccination, according to the MedDRA classification, in all subjects and in all groups. SAEs. 
 Occurrence of SAEs from Dose 1 (Day 1) up to study end, in all subjects and in all groups. AEs of specific interest. 
 Occurrence of AEs of specific interest (pIMDs) from Dose 1 up to study end, in all subjects and in all groups. Laboratory parameters 
 Occurrence of hematological (white blood cells, platelets count, and hemoglobin level) and biochemical (alanine aminotransferase, aspartate aminotransferase, creatinine, and uric acid) laboratory abnormalities at Screening, Days 8, 31, 38, 180, 390, 476, 491, 498, and 670 and urinary laboratory abnormalities (protein, glucose, and blood) at Screening. (Grades will be based on the local laboratory normal ranges and derived from the FDA Toxicity Grading Scale for laboratory abnormalities).

Table 9 Study Objectives and Endpoints

Objectives	Endpoints
Secondary	

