- **Step 3:** Vaccination of approximately 30 subjects aged 50-70 years (approximately 10 subjects in the CDIFF Ag group, approximately 10 subjects in the CDIFF Ag + an adjuvant system containing 3-O-desacyl-4'-monophosphoryl lipid A [MPL], QS-21 and liposome [50 µg MPL and 50 µg QS-21] AS01B group, and approximately 10 subjects in the placebo group). An iSRC will review all accumulating safety data after Dose 1, and then after Dose 2. Vaccination in Step 4 will proceed in the absence of a safety concern detected by the iSRC on all accumulating safety data at the end of Step 3.

- **Step 4:** Vaccination of approximately 70 subjects aged 50-70 years (approximately 25 subjects in the CDIFF Ag group, approximately 35 subjects in the CDIFF Ag + AS01_B group, and approximately 10 subjects in the placebo group). An iSRC will review all accumulating safety data 3 weeks after the start of vaccination in Step 4 and then about every 3 weeks until all subjects have received Dose 1. In addition, the iSRC will review all safety data after Dose 2 (refer to Section 8.11 for study procedures to be considered during special circumstances). A subcohort of subjects who have successfully completed all visits up to Visit 7, have received two doses on an active arm (ie, the subjects who received placebo will be excluded), do not meet any contraindication for subsequent vaccination, and still meet the eligibility criteria will receive a third dose after the iSRC has reviewed all the accumulating safety data at the end of Step 4 Dose 2. If there are any safety concerns observed during SRT reviews post Dose 3, an ad hoc iSRC meeting will take place to review the unblinded safety data.

Refer to Section 9.6 for iSRC oversight.

During all 4 steps, all subjects should be closely observed for at least 60 minutes after vaccination.

For Steps 1, 2, and 3 only, all subjects should be vaccinated sequentially and at least 60 minutes apart to allow for monitoring of any acute events (eg, hypersensitivity reaction).

During vaccination days of Steps 1, 2, and 3 (ie, Day 1 and Day 31), vaccination will be limited to a maximum of 10 subjects per day. In Step 4, there is no limit related to the number of subjects to be vaccinated per day.

Table 10 Study Groups Foreseen in the Study (Refer to Section 8.11 for Study Procedures to be Considered During Special Circumstances)

Step	Study Groups	Number of Subjects	Age (Minimum/Maximum)
1	Placebo	10	18-45 years
	CDIFF Ag	10	18-45 years

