In case an emergency mass vaccination for an unforeseen public health threat (eg, a pandemic) is recommended and/or organized by public health authorities outside the routine immunization program, the time period described above can be reduced if, necessary for that vaccine, provided it is used according to the local governmental recommendations and that the Sponsor is notified accordingly.
9. Planned administration of GSK's Herpes Zoster vaccine marketed as *Shingrix* or an adjuvanted recombinant varicella zoster virus envelope gE subunit vaccine (HZ/su) within 180 days before the first dose and within 180 days after the last dose of the study vaccine.
10. Planned elective surgery during the study period.

11. Concurrently participating in another clinical study, at any time during the study period, in which the subject has been or will be exposed to an investigational or a non-investigational vaccine/product (pharmaceutical product or device).
12. Body mass index $<19 \text{ kg/m}^2$ or $\geq 35 \text{ kg/m}^2$.
13. Clinically relevant physical examination abnormalities.
14. For subjects aged 18–45 years, Grade 2 or higher abnormal hematological, biochemical, and urinary parameters.
15. For subjects aged 50–70 years, Grade 3 or higher abnormal hematological, biochemical, and urinary parameters.
16. Documentation of current or prior episode of CDI.
17. Any confirmed or suspected immunosuppressive or immunodeficient condition, based on medical history and physical examination (no laboratory testing required).
18. Recurrent history or uncontrolled neurological disorders or seizures.
19. Family history of congenital or hereditary immunodeficiency.
20. History of any reaction or hypersensitivity likely to be exacerbated by any component of the vaccines.
21. Acute disease and/or fever at the time of enrollment.
 - Fever is defined as temperature $\geq 38.0^\circ\text{C}/100.4^\circ\text{F}$. The preferred location for measuring temperature in this study will be the oral cavity.
 - Subjects with a minor illness (such as mild diarrhea, mild upper respiratory infection) without fever may, be enrolled at the discretion of the Investigator.
22. Acute or chronic, clinically significant pulmonary, cardiovascular, hepatic, or renal functional abnormality, as determined by physical examination or laboratory screening tests.
23. Pregnant or lactating female.
24. History of intestinal bleeding or history of diverticular intestinal bleeding.

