- The maximum grading from Screening up to Visit 5 (Day 61)/Visit 7 (Day 390) for subjects receiving 2 doses/Visit 11 (Day 670) for subjects receiving a third dose will be tabulated (grades will be based on local laboratory normal ranges and derived from Food and Drug Administration [FDA] Guidance to Industry “Toxicity Grading Scale for Healthy Adult and Adolescent Volunteers Enrolled in Preventive Vaccine Clinical Trials” [refer to [Table 13](#)]). Those laboratory parameters not included in the FDA grading scale will not be graded).

The percentage of subjects using concomitant medication (any medication, any antipyretic and any antipyretic taken prophylactically, respectively) during the 7-day follow-up period and during the 30-day follow-up period will be summarized by group after each vaccination and overall.

Separate safety summaries for Subcohort Set may be generated as appropriate.

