**Step 4:** Vaccination of approximately 70 subjects aged 50-70 years (approximately 25 subjects in the CDIFF Ag group, approximately 35 subjects in the CDIFF Ag + AS01B group, and approximately 10 subjects in the placebo group). An iSRC will review all accumulating safety data 3 weeks after the start of vaccination in Step 4 and then about every 3 weeks until all subjects have received Dose 1. In addition, the iSRC will review all safety data after Dose 2. A subcohort of subjects who have successfully completed all visits up to Visit 7, have received two doses on an active arm (ie, the subjects who received placebo will be excluded) do not meet any contraindication for subsequent vaccination, and still meet the eligibility criteria will receive a third dose after the iSRC has reviewed all the accumulating safety data at the end of Step 4 Dose 2. If there are any safety concerns observed during SRT reviews post Dose 3, an ad hoc iSRC meeting will take place to review the unblinded safety data.

During all 4 steps, all subjects should be closely observed for at least 60 minutes after vaccination. For Steps 1, 2, and 3 only, all subjects should be vaccinated sequentially and at least 60 minutes apart to allow for monitoring of any acute events (eg, hypersensitivity reaction). During vaccination days of Steps 1, 2, and 3 (ie, Day 1 and Day 31), vaccination will be limited to a maximum of 10 subjects per day. A total of 120 subjects aged 50 – 70 years (30 receiving placebo, 45 receiving CDIFF Ag and 45 receiving CDIFF Ag + AS01B) and 20 subjects aged 18-45 years (10 receiving placebo and 10 receiving CDIFF Ag) will be enrolled in this study. The duration of the study for each subject receiving 2 doses will be approximately 1 year (Visit 7) and each subject receiving 3 doses will be approximately 2 years (Visit 11).

Study treatment will be administered as indicated below:

Document:	\\usadc-nas01a\cp_ops\PROJECTS\Glaxo SmithKline\GSK208109_BZA47109\SAP		
Author:	PPD	Version Number:	3.0

Template No: CS\_TP\_BS016 – Revision 5  
Effective Date: 01Apr2018

[figure not shown]
Reference: CS\_WI\_BS005

Type of Contact and Timepoint	Study Group	Treatment Name	Volume to be Administered	Route	Injection Site	
					Location	Laterality a
Visit 1 (Day 1)	Placebo	Placebo	0.5 mL	IM	Deltoid	Nondominant
	CDIFF Ag	CDIFF Ag	0.5 mL	IM	Deltoid	Nondominant
	CDIFF Ag + AS01 B	CDIFF Ag + AS01 B	0.5 mL	IM	Deltoid	Nondominant

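### The maximum laboratory grade is counted from Screening, so grades allowed at entry appear as outcomes; if its later cut-off is pooled by arm, only the active arms aged 50-70 have the longer window

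*SAP*

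**What the plan says.** SAP 16.2 plans, for each group and each hematology, biochemistry and urinalysis parameter, a table of "The maximum grading from Screening up to Visit 5 (Day 61"), then to Day 390 for two-dose subjects and to Day 670 for those given a third dose. Protocol 9.4.2.1 has the same rule: "The maximum grading from Screening up to Visit 5 (Day 61)/Visit 7 (Day 390) for subjects receiving 2 doses/Visit 11 (Day 670"). The SAP therefore does not depart from the protocol.

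The related text is:

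- **Endpoint (protocol 3.0, Table 9).** Laboratory abnormality is part of the primary safety endpoint. Blood parameters are listed as "laboratory abnormalities at Screening, Days 8, 31, 38, 180, 390, 476, 491, 498, and 670", and urine as "urinary laboratory abnormalities (protein, glucose, and blood) at Screening". Protocol Tables 6 and 25 add one urinalysis, at the Dose 3 screening (Day 476).
- **Entry (protocol 5.2).** Subjects aged 50-70 are excluded for "Grade 3 or higher abnormal hematological, biochemical, and urinary parameters". Subjects aged 18-45 are excluded from Grade 2 upward.
- **Dose 3 (SAP 3.1).** It goes to Step 4 subjects who "have received two doses on an active arm (ie, the subjects who received placebo will be excluded"). The active part of Step 4 is "approximately 25 subjects in the CDIFF Ag group, approximately 35 subjects in the CDIFF Ag + AS01_B group" (protocol 4.1).
- **Display (SAP 6.2).** Data are generally shown by age stratum and treatment, with no split by step or number of doses.

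**The concern.** A maximum-grade table is read as a summary of what happened after vaccination. Two features of this one work against that reading.

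1. Its start point is before the first dose. A subject aged 50-70 who enters with a stable Grade 2 value, or whose Grade 2 value then returns to normal, is reported with a maximum of Grade 2.
2. Its later end point depends on the number of doses received, and dose number is tied to treatment because no placebo subject can receive a third dose. If two-dose and three-dose subjects share a column, the active columns at 50-70 years contain more sampling occasions than the placebo column. The two active columns also differ from each other.

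Safety is descriptive, so these percentages, read beside the placebo control, are the evidence. No committed output gives a post-vaccination grade or a shift in grade. The by-timepoint table shows in-range or out-of-range status only. The protocol makes separate subcohort safety summaries optional. The SAP defines change from baseline for laboratory parameters (6.6), but 16.2 lists no such laboratory table.

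**Working it through.** **Figure stated in the plan.** The documents give no figure for this table. The nearest is protocol 9.2: with 45 subjects, an 80% or 90% probability of seeing at least one event at true rates of 3.5% or 5.0%. It reproduces: 1 − 0.965^45 = 79.9% and 1 − 0.95^45 = 90.1%. The same form, 1 − (1 − p)^k, is used below with k scheduled draws in one subject.

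**Scheduled blood draws (protocol Tables 6 and 25)**

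| Window | Draws | Total | After Dose 1 |
|---|---|---|---|
| To Day 61, all arms | Screening, Days 8, 31, 38 | 4 | 3 |
| To Day 390, two doses | adds Days 180, 390 | 6 | 5 |
| To Day 670, three doses | adds Days 476, 491, 498, 670 | 10 | 9 |

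Days 476 and 491 come before Dose 3. Day 1 sampling is an optional retest and is not counted.

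**Effect of including Screening.** Assume 10% of subjects have an allowed grade at Screening and a 1% chance per later draw, independent of the Screening grade. Neither figure is in the documents. For a two-dose subject:

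- from Screening: 1 − 0.90 × 0.99^5 = 14.4%
- after vaccination only: 1 − 0.99^5 = 4.9%

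For urinalysis no assumption is needed. A two-dose subject has one scheduled sample, and it precedes vaccination.

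**Effect of unequal windows, if dose groups are pooled.** At 50-70 years the groups are 30 placebo, 45 CDIFF Ag and 45 CDIFF Ag + AS01B. At most 25/45 (56%) and 35/45 (78%) of the active groups reach Day 670; for placebo it is 0/30. Let a = 1 − (1 − p)^5 and b = 1 − (1 − p)^9. Then placebo = a, CDIFF Ag = (20a + 25b)/45 and CDIFF Ag + AS01B = (10a + 35b)/45. With the same p in every arm (no vaccine effect) and independent draws:

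| p per draw (assumed) | a | b | Placebo | CDIFF Ag | CDIFF Ag + AS01B |
|---|---|---|---|---|---|
| 1% | 4.9% | 8.6% | 4.9% | 7.0% | 7.8% |
| 2% | 9.6% | 16.6% | 9.6% | 13.5% | 15.1% |
| 5% | 22.6% | 37.0% | 22.6% | 30.6% | 33.8% |

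At 2% the gaps from placebo are 3.9 and 5.5 percentage points.

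**Within-subject correlation.** Repeated values in one person are not independent. Under a beta-binomial model with correlation ρ and s = (1 − ρ)/ρ, the probability of no abnormality in k draws is the product over i = 0 to k − 1 of ((1 − p)s + i)/(s + i). At p = 2%:

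| ρ | Placebo | CDIFF Ag | CDIFF Ag + AS01B | AS01B − placebo |
|---|---|---|---|---|
| 0 | 9.6% | 13.5% | 15.1% | 5.5 |
| 0.3 | 5.9% | 7.1% | 7.5% | 1.6 |
| 0.6 | 3.9% | 4.3% | 4.5% | 0.6 |

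The size depends on p and ρ; the direction does not.

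**The case against.** The strongest reply is that the plan already has an equal window and does not say that unequal ones will be mixed.

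- **Day 61 cut-off.** It carries no dose condition, and every arm has the same four draws. This stands: the arms are not unequally observed at that cut-off, although it still starts at Screening.
- **Pooling is not certain.** The slash-separated sentence can be read as separate tables by number of doses. This stands as an ambiguity. SAP 6.2 points towards pooling, and the analysis-set table in SAP 5.6 assigns laboratory data to the Exposed Set without listing the Subcohort Exposed Set.
- **The endpoint is by timepoint.** The by-timepoint table separates Screening from later days and compares arms on equal days, and individual profiles are plotted. This lessens the consequence, but the table gives range status, not grade, and profiles are not counts.
- **Other safeguards exist.** Holding rule 2d uses only Grade 3 abnormalities within 7 days after vaccination. Clinically significant findings present at the start that do not worsen are not reported as adverse events. Protocol Table 13 has hemoglobin rows for change from baseline. These protect other outputs, not this table.
- **Entry limits carry-over.** It is confined to Grade 1 or Grades 1-2, eligibility deviations aside, so Grade 3 counts are essentially unaffected. Randomization makes it similar across arms in expectation: it dilutes a signal and does not create a vaccine excess.
- **No safety tests are planned.** True, so no error rate is affected. The issue is how a descriptive table will be read.

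**Conclusion.** The start at Screening is a definite defect of the table as written: it mixes low grades allowed at entry with outcomes, and for two-dose urinalysis it contains nothing else. The unequal later window is a conditional defect, arising only if two-dose and three-dose subjects are pooled within the 50-70 arms. In that case, at an assumed 2% per draw with independent draws and full Dose 3 uptake in Step 4, rates of about 9.6%, 13.5% and 15.1% would appear with no vaccine effect. Correlation of 0.3 to 0.6 cuts the largest gap from 5.5 points to between 1.6 and 0.6.

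A reader might infer more than the documents support:

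- A 7-point gap between arms. At 2%, 16.6% against 9.6% compares three-dose with two-dose subjects; active arms are mixtures of the two.
- That active subjects in general have more chances to show an abnormality. Those aged 18-45 and those in Steps 2 and 3 have the same Day 390 window as placebo.
- That each Screening grade adds one subject to the count. It does so only if no equal or higher grade occurs later.

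The change is worth making before the tables are produced.

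**What to change.** In SAP 16.2, replace the maximum-grade item with:

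1. Maximum post-vaccination grade (Day 8 onward) in two separate tables, to Day 61 and to Day 390, for all arms. Each is cross-tabulated against the baseline grade. Under the SAP 6.5 fallback rule, baseline will usually be the Screening value, since Day 1 sampling is optional.
2. For the Subcohort Exposed Set only, maximum grade over Days 498-670 against the last pre-Dose 3 value.
3. Day 476 and Day 491 grades reported by timepoint as pre-Dose 3 values, so that no draw named in the endpoint is lost.
4. Screening urinalysis reported as a baseline characteristic.

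With item 1 every arm has five post-vaccination draws to Day 390, so with no vaccine effect the expected rates are equal (9.6% at 2% per draw, independent draws). State explicitly that two-dose and three-dose windows are not combined in one column, and align protocol 9.4.2.1 or record the change in SAP 3.3. The cost is SAP wording and table shells. The data are already collected and the baseline rule already exists.

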1.3 Schedule of Activities

Table 6 Schedule of Activities (Refer to Section 8.11 for Study Procedures to be Considered During Special Circumstances)

Type of contact	Screening ^a	Visit 1	Visit 2	Visit 3	Visit 4	Visit 5	Visit 6	Visit 7	Screening for Dose 3, Step 4	Visit 8 for Step 4	Visit 9 for Step 4	Visit 10 for Step 4	Visit 11 for Step 4
Timepoints	Day -15	Day 1	Day 8	Day 31	Day 38	Day 61	Day 180	Day 390	Day 476	Day 491	Day 498	Day 521	Day 670
Informed consent	●												
Informed consent addendum									●				
Check inclusion/exclusion criteria	●	●							●				
Collect demographic data ^b	●												
Medical history ^c	●												
Physical examination	●	● ^e	○ ^d	● ^e	○ ^d	○ ^d	○ ^d	○ ^d	●	● ^e	○ ^d	○ ^d	○ ^d
Vital signs (systolic/diastolic blood pressure and heart rate)	●	● ^e	○	● ^e	○	○	○	○	●	● ^e	○	○	○
Urine pregnancy test ^f	●	● ^e		● ^e					●	● ^e			
Measure/record height and weight	●												
Check contraindications to subsequent vaccination ^g				● ^e						● ^e			
Body temperature		● ^e		● ^e						● ^e			
Study group and treatment number allocation		○ ^e											
Treatment number allocation for subsequent dose				○ ^e						○ ^e			

Table 6 Schedule of Activities (Refer to Section 8.11 for Study Procedures to be Considered During Special Circumstances)

Type of contact	Screening ^a	Visit 1	Visit 2	Visit 3	Visit 4	Visit 5	Visit 6	Visit 7	Screening for Dose 3, Step 4	Visit 8 for Step 4	Visit 9 for Step 4	Visit 10 for Step 4	Visit 11 for Step 4
Timepoints	Day -15	Day 1	Day 8	Day 31	Day 38	Day 61	Day 180	Day 390	Day 476	Day 491	Day 498	Day 521	Day 670
Recording of administered treatment number		●		●						●			
Vaccine administration		●		●						●			
Blood sampling for antibody determination (humoral immunogenicity) (approximately 20 mL) – TNA and ELISA		● ^e		● ^e		●	●	●		● ^e		●	●
Optional blood sample for PBMC isolation (approximately 40 mL)						● ^k							
Blood sampling for hematology and biochemical analysis (approximately 5.5 mL) ^{h, i}	●	● ^{e, j}	●	● ^e	●		●	●	●	● ^e	●		●
Urine analysis (quantitative or semi-quantitative analysis)	●								●				
Record any concomitant medications/vaccinations	●	● ^e	●	● ^e	●	●	●	●	●	● ^e	●	●	●
Record any intercurrent medical conditions	●	● ^e	●	● ^e	●	●	●	●	●	● ^e	●	●	●
Distribution of the subject card	○												
Distribution of paper diary cards		○		○						○			

Table 6 Schedule of Activities (Refer to Section 8.11 for Study Procedures to be Considered During Special Circumstances)

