6.2 Contraindication to Subsequent Vaccination

Prior to receipt of additional study vaccination, subjects must be evaluated to confirm that they are eligible for subsequent vaccination.

If subjects meet any of the original exclusion criteria or the criteria listed below, they should not receive additional vaccinations. However, the subjects should be encouraged to continue other study procedures at the discretion of the Investigator (Section [8.3.3](#)).

- Subjects who experience any SAE judged to be possibly or probably related to study vaccine or non-study vaccines, including hypersensitivity reactions.

- Subjects who develop any new condition which, in the opinion of the Investigator, may pose additional risk to the subject if he/she continues to participate in the study.
- Anaphylaxis following the administration of vaccines.
- Grade 3 or higher abnormal hematological, biochemical, and urinary parameters.
- Occurrence of a new potential immune-mediated disease (pIMD) or the exacerbation of an existing pIMD that, in the opinion of the Investigator, expose the subject to unacceptable risk from subsequent vaccination. In such cases, the Investigator should use his/her clinical judgment prior to administering the next dose of the vaccine(s)/product(s). Refer to [Appendix 2](#) for the definition of pIMDs.

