9.4.2 Safety Analyses

9.4.2.1 Primary Analyses

The primary analysis will be performed on the Exposed Set.

The percentage of subjects with at least 1 local AE (solicited and unsolicited), with at least 1 general AE (solicited and unsolicited) and with any AE during the 7-day or the 30-day follow-up period will be tabulated with exact 95% CI after each vaccination and overall. The percentage of doses followed by at least 1 local AE (solicited and unsolicited), by at least 1 general AE (solicited and unsolicited) and by any AE will be tabulated, overall vaccination course, with exact 95% CI. The same computations will be done for Grade 3, any AEs considered related to vaccination and any Grade 3 AEs considered related to vaccination.

The percentage of subjects/doses reporting each individual solicited local and general AE during the 7-day follow-up period will be tabulated with exact 95% CI as follows:

- Over the 2 or 3 doses, the percentage of subjects with the symptom and its exact 95% CI.
- Over the 2 or 3 doses, the percentage of doses with the symptom and its exact 95% CI.
- At each study dose (visit), the percentage of subjects with the symptom and its exact 95% CI.

Occurrence of fever will be reported per 0.5°C cumulative increments as from $\geq 38^{\circ}\text{C}$ as well as the occurrence of fever $>40^{\circ}\text{C}/104^{\circ}\text{F}$ with causal relationship to the study treatment.

The verbatim reports of unsolicited symptoms will be reviewed by a physician and the signs and symptoms will be coded according to the Medical Dictionary for Regulatory Activities (MedDRA). Every verbatim term will be matched with the appropriate preferred term. The percentage of subjects with unsolicited AEs within 30 days after any doses with its exact 95% CI will be tabulated by group and by MedDRA preferred term. Similar tabulation will be done for Grade 3 unsolicited AEs, for unsolicited AEs that resulted in a medically attended visit, for Grade 3 and causally related unsolicited AEs and for unsolicited AEs causally related to vaccination.

The number of subjects who experienced at least 1 SAE or any AE of specific interest (pIMD) during the entire study period will be reported.

For each group and for each hematology, biochemistry, and urinalysis parameter:

- The percentage of subjects having hematology, biochemistry, and urinalysis results below or above the local laboratory normal ranges will be tabulated by timepoint.

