Given the multitude of the immunogenicity assays (TNA with different cell lines), the interim analysis may be performed in several parts upon the availability of assay results (until Day 61 or Day 521). The first part will include the available immunogenicity assay results (until Day 61 or Day 521) and safety data available. The subsequent parts will include only additional data results of immunogenicity assays that become available later. Any immunogenicity data (until Day 61 or Day 521) that become available at the end of the study will be included in the final (end of study) analysis.

All analyses are descriptive and with the aim to characterize the safety and immunogenicity data and therefore no statistical adjustment for interim analysis is required.

Derivations and definitions for the interim analyses will be based on those required for the final analysis contained in this analysis plan, unless deviations are stated within the text.

All tables presenting summary statistics planned for final analysis will be generated at the time of interim analyses, only for the primary cohort (exposed set for safety and per protocol set/full analysis set for immunogenicity analyses). No unblinded individual subject listings and listing tables will be generated at the time of interim analyses.

CCI

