#### 5.2.3. SUBCOHORT EXPOSED SET

The subcohort exposed set will contain all subjects who have received the Dose 3 on an active arm.

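### The maximum-grade laboratory table omits Dose 3 screening grades (Day 476) in subjects screened but not dosed, including a Grade 3 result that itself stopped the dose

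*SAP*

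**What the plan says.** **Window.** SAP 16.2 and Protocol 9.4.2.1 use the same rule for the maximum-grade table. It starts at Screening and closes at Day 61 or, beyond that, at "Visit 7 (Day 390) for subjects receiving 2 doses/Visit 11 (Day 670) for subjects receiving a third dose will be tabulated". Neither document gives a window for a subject screened for Dose 3 but not dosed.

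**Bar to Dose 3.** Protocol 6.2 lists among the contraindications "Grade 3 or higher abnormal hematological, biochemical, and urinary parameters". Exclusion criterion 15 (Protocol 5.2) sets the same limit for ages 50-70, and Protocol 4.1 requires that eligibility still be met before Dose 3.

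**Timepoints.** The primary laboratory endpoint (Protocol 3.0, Table 9) covers blood abnormalities "at Screening, Days 8, 31, 38, 180, 390, 476, 491, 498, and 670 and urinary laboratory abnormalities (protein, glucose, and blood) at Screening". In Table 6 the row "Urine analysis (quantitative or semi-quantitative analysis)" is marked only at Screening and at the Dose 3 screening visit.

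**Who is screened.** Only Step 4 active-arm subjects: "approximately 25 subjects in the CDIFF Ag group, approximately 35 subjects in the CDIFF Ag" plus AS01B group (Protocol 4.1).

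**Other laboratory outputs.** Both documents also plan a table in which "results below or above the local laboratory normal ranges will be tabulated by timepoint". SAP 16.2 adds individual profiles for hematology and biochemistry, and a Grade 3/4 summary limited to subjects with COVID-19 infection. SAP 5.6 assigns laboratory data to the Exposed Set. For subcohort summaries, SAP 5.2.3 says: "The subcohort exposed set will contain all subjects who have received the Dose 3 on an active arm". At the interim analyses, SAP 4.3 says: "No unblinded individual subject listings and listing tables will be generated at the time of interim analyses".

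**The concern.** A safety table should not leave out a result because of how bad the result was. Here the window is set by receipt of Dose 3, and receipt of Dose 3 depends in part on the Day 476 laboratory grades. A disqualifying grade keeps the subject in the two-dose category, and that category closes 86 days earlier on the nominal calendar (476 - 390 = 86). The subject stays in the Exposed Set and is shown with the maximum up to Day 390.

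Day 476 blood results are a named timepoint of a primary endpoint, and the maximum-grade table is the only planned graded summary that is not limited to COVID-19 cases. What is at stake is whether a reader of the summary tables can see the laboratory grades that led to Dose 3 being withheld.

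**Working it through.** The plan states no figure to reproduce. The check is a trace of the rules and a count.

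**1. Trace.** Grade 3 or higher at Day 476 → contraindicated (Protocol 6.2) and ineligible (criterion 15) → no third dose → two-dose subject → window closes at Day 390 → the Day 476 grade is not counted. A subject who misses Dose 3 for another reason, such as refusal or another contraindication, loses the Day 476 grade in the same way, whatever it was. Among subjects dosed in line with the protocol, the recorded Day 476 value is below Grade 3. The table therefore cannot show a Grade 3 result from Day 476 unless there is a deviation.

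**2. Scheduled results per subject** (Table 6; optional Day 1 retest not counted). Blood up to Day 390: Screening and Days 8, 31, 38, 180, 390 = 6. Day 476 makes 7. Days 491, 498 and 670 make 10.

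| Subject | Blood: total / inside / outside | Urine: total / inside / outside |
|---|---|---|
| Received Dose 3 | 10 / 10 / 0 | 2 / 2 / 0 |
| Screened, not dosed, no Day 491 sample | 7 / 6 / 1 | 2 / 1 / 1 |
| Screened, not dosed, Day 491 sample taken | 8 / 6 / 2 | 2 / 1 / 1 |
| Never screened for Dose 3 | 6 / 6 / 0 | 1 / 1 / 0 |

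The third row is possible because Day 491 blood is drawn before vaccination, at the visit where contraindications are checked again. Protocol 6.2 also encourages undosed subjects to continue other procedures.

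**3. Can the grade be seen elsewhere?**
- By-timepoint table: Day 476 is included with no dose restriction, but only as below or above normal range.
- Profiles: hematology and biochemistry parameters with an FDA scale only; no urine.
- Subcohort Exposed Set: dosed subjects only.
- AE tables: unsolicited AEs are tabulated within 30 days of a dose, so a non-serious finding at Day 476 would normally be missed.
- Listings: at the final analysis, but no unblinded listings at the second interim analysis.

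**4. Number and timing.** Subjects who can be affected: 25 + 35 = 60 on planned numbers, none on placebo. Days from Dose 2 to Dose 3 screening: nominal 476 - 31 = 445. Using the Table 7 intervals, the minimum is 350 + 20 = 370 and the maximum is 395 + 150 = 545.

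**5. Size if it happens.** If the table pools all 45 subjects aged 50-70 in an active arm, each omitted subject with no earlier Grade 3 for that parameter lowers the arm's Grade 3 percentage by 1/45 = 2.2 points. If two-dose and three-dose subjects are tabulated separately, the denominator differs. The table shells are not among the documents, so this figure is conditional.

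**6. Illustration only.** The documents give no Grade 3 rate at Day 476. Assume a rate p of 0.5% to 5% per subject, with 60 screened. The expected number omitted is 60p = 0.3 to 3.0. The chance of at least one is 1 - (1 - p)^60 = 26% to 95%.

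**The case against.** The strongest reply is that the cut-off follows the design. Study conclusion for two-dose subjects is Day 390, and Protocol 5.4 treats someone who consents but is not given Dose 3 as a screen failure with a separate reporting path: failure details, eligibility criteria and SAEs. SAP 9 plans a listing of inclusion/exclusion responses. Keeping eligibility-screen values out of a follow-up maximum is defensible. This stands as a reason not to alter the window. It does not restore a graded summary, since neither the screen-failure information nor the eligibility listing is one, and SAP 9 names no count of subjects screened against subjects dosed for Dose 3.

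Four further limits stand:
- The rule depends on dose receipt, not on grade as such. Only at Grade 3 or higher does the result cause its own omission.
- If the single rescreening in Protocol 5.4 applies to Dose 3 (the text is not explicit), only the repeat laboratory result is recorded. A transient first Grade 3 would then be missing from the eCRF, and no table could recover it.
- The urinary endpoint is defined at Screening only, and holding rule 2d covers blood in the 7 days after a dose. Parameters outside the FDA scale are not graded. For urine the matter is mostly labelling.
- Ending the window at the last available result for everyone would add a chance of a high grade only in the Step 4 active arms, and so would worsen comparability with placebo.

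A reader might infer that a disqualifying Grade 3 disappears from reporting. The documents do not support that: the value appears ungraded by timepoint on the Exposed Set, including at the second interim analysis, and with its size in the blood profiles and final listings.

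**Conclusion.** The point holds, at low severity. Under the written rule, any Day 476 grade, and any Day 491 pre-dose grade, in a Step 4 active-arm subject who is screened but not dosed is left out of the maximum-grade table. For Grade 3 or higher, the omission is caused by the outcome.

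This rests on a literal reading of the window and on Protocol 6.2 being followed. The number of results affected is unknown. The analysis is descriptive, with no hypothesis tested, and a result 370 to 545 days after Dose 2 is weak evidence about Doses 1 and 2. A reader might go further and conclude that the vaccine's laboratory safety profile is materially understated; nothing in the documents shows that. The defect is one missing graded summary at a named endpoint timepoint.

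**What to change.** Leave the maximum-grade windows in SAP 16.2 and Protocol 9.4.2.1 unchanged. Add a separate graded row or table, 'Dose 3 screening (Day 476), all screened', by active arm:
- recorded hematology, biochemistry and gradable urinalysis results for every subject screened, dosed or not;
- the number screened and the number dosed;
- any Day 491 pre-dose result in subjects not dosed;
- a footnote that rescreened subjects may contribute only the repeat value.

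Do not extend the window to the last available result for all subjects. Labelling urine grades as 'Screening (before Dose 1)' and 'Day 476 (before Dose 3)' is optional.

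The cost is one table shell and one sentence in each document, before the second interim analysis if it has not been run and otherwise before the final analysis. No new sample, visit or eCRF item is needed: Table 6 already marks Day 476 blood and urine and Day 491 blood for eCRF entry.
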